4.1 Survival Follow-up

Once a patient completes 6 cycles of therapy and/or is off study due to any reason, no further clinical and survival follow up is required.

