17.0 Pathology Considerations/Tissue Biospecimens NA.....	58
18.0 Records and Data Collection Procedures.....	58
19.0 Budget.....	59
20.0 References.....	60
Appendix I ECOG Performance Status.....	62

Schema

*Sample collection under IRB#14-009163, IRB#919-04, or IRB#521-93

**Dosing and regimen as per section 7

***Patients who discontinue treatment before completing 6 cycles for any reason will go off study (No SFU/CFU).

[†]Cycle 1 = 21. Cycles 2 – 6 = 28 days

Generic name: Lenalidomide	Generic name: Pomalidomide	Generic name: Dexamethasone
Brand name(s): Revlimid	Brand name(s): Pomalyst	Brand name(s):
Mayo Abbreviation:	Mayo Abbreviation:	Mayo Abbreviation:
Availability: Commercial	Availability: Commercial	Availability: Commercial

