9.0 Ancillary Treatment/Supportive Care

9.1 Full supportive care

Patients should receive full supportive care while on this study. This includes blood product support, antibiotic treatment, and treatment of other newly diagnosed or concurrent medical conditions. All blood products and concomitant medications such as antidiarrheals, analgesics, and/or antiemetics received from the first day of study treatment administration until 30 days after the final dose will be recorded in the medical records.

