10.52 Death

Note: A death on study requires both routine and expedited reporting regardless of causality, unless as noted below. Attribution to treatment or other cause must be provided.

Any death occurring within 30 days of the last dose, regardless of attribution to an agent/intervention under an IND requires expedited reporting within 24-hours.

Any death occurring greater than 30 days with an attribution of possible, probable, or definite to an agent/intervention under an IND requires expedited reporting within 24-hours.

Reportable categories of Death

- Death attributable to a CTCAE term.
- Death Neonatal: A disorder characterized by cessation of life during the first 28 days of life.
- Death NOS: A cessation of life that cannot be attributed to a CTCAE term associated with Grade 5.
- Sudden death NOS: A sudden (defined as instant or within one hour of the onset of symptoms) or an unobserved cessation of life that cannot be attributed to a CTCAE term associated with Grade 5.
- Death due to progressive disease that cannot be attributed to a CTCAE term associated with Grade 5 should be reported as **Grade 5 “Disease progression”** under the system organ class (SOC) of General disorders and administration site conditions. Evidence that the death was a manifestation of underlying disease (e.g., radiological changes suggesting tumor growth or progression: clinical deterioration associated with a disease process) should be submitted.

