10.62 All other AEs

Submit via appropriate MCCC Case Report Forms (i.e., paper or electronic, as applicable) the following AEs experienced by a patient and not specified in Section 10.6:

10.621 Grade 2 AEs deemed *possibly, probably, or definitely* related to the study treatment or procedure.

10.622 Grade 3 and 4 AEs regardless of attribution to the study treatment or procedure.

10.623 Grade 5 AEs (Deaths)

10.6231 Any death within 30 days of the patient’s last study treatment or procedure regardless of attribution to the study treatment or procedure.

10.6232 Any death more than 30 days after the patient’s last study treatment or procedure that is felt to be at least possibly

treatment related must also be submitted as a Grade 5 AE, with a CTCAE type and attribution assigned.

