13.0 Treatment/Follow-up Decision at Evaluation of Patient

- 13.1 Off protocol treatment

Patients who go off protocol treatment before completing 6 cycles of treatment will not continue to be followed.
- 13.2 Criteria for Treatment Discontinuation

Patients may discontinue treatment for the following reasons:

 - Progressive multiple myeloma (see Section 11.0)
 - Patient withdraws consent to continue in the trial
 - Patient develops an intercurrent illness that precludes further participation, or requires a prohibited concomitant treatment
 - The Investigator withdraws the patient in the patient's best interests
 - Patient is lost to follow-up (defined as the inability to contact the patient on 3 separate occasions)
 - Administrative reasons (e.g., the patient is transferred to hospice care)
 - An adverse event, which in the opinion of the investigator precludes further trial participation

Patients will be taken off study if they discontinue treatments for any of the reasons above.

- 13.3 Criteria for Study Discontinuation

The study may be temporarily or permanently discontinued at any site and at any time. Reasons for study discontinuation may include, but are not limited to, the following:

 - Safety concerns
 - Non-compliance with the protocol, Good Clinical Practice guidance or other regulatory requirements by the Investigator(s)
 - Request to discontinue the trial by a regulatory or health authority or an IRB

- 134 Ineligible

A patient is deemed *ineligible* if after registration, it is determined that at the time of registration, the patient did not satisfy each and every eligibility criteria for study entry.

- If the patient received treatment, the patient may continue treatment at the discretion of the physician as long as there are not safety concerns. The patient will continue in the Active Monitoring/Treatment phase of the study, as per section 4.0 of the protocol.
- If the patient never received treatment, on-study material must be submitted. No further data submission is necessary.

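### Follow-up ends when a patient goes off study, but adverse events and deaths must be reported for 30 days after the last dose and no contact is scheduled to find them

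*Combined protocol and SAP*

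**What the plan says.** Three places end follow-up. Section 4.1 says that after six cycles, or once a patient is off study for whatever reason, "no further clinical and survival follow up is required". Section 13.1: "Patients who go off protocol treatment before completing 6 cycles of treatment will not continue to be followed". A schema footnote repeats this for anyone who stops before six cycles, whatever the reason. An adverse event is one of the listed reasons in 13.2, which closes: "Patients will be taken off study if they discontinue treatments for any of the reasons above". Section 8.1 also sends patients off study directly for several severe toxicities, such as grade 3 or higher arrhythmia and grade 4 anaphylaxis.

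The last column of the Section 4 schedule is End of Treatment, with a window of ±7 days. It includes an adverse event assessment, physical exam, hematology and chemistry. No later contact is listed.

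Other sections look 30 days past the last dose:

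- 10.41 sets expedited reporting for adverse events within 30 days of the last administration. Its first footnote extends the duty beyond 30 days for serious events judged at least possibly related.
- 10.6231 requires routine reporting of any death within 30 days of the "last study treatment or procedure regardless of attribution to the study treatment or procedure".
- 10.52 states: "Any death occurring within 30 days of the last dose, regardless of attribution to an agent/intervention under an IND requires expedited reporting" within 24 hours.
- 9.1 asks that blood products and concomitant medications "received from the first day of study treatment administration until 30 days after the final dose will be recorded in the medical records".

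**The concern.** Sections 9.1 and 10 ask for information over a window in which, under 4.1, 13.1 and the schema, nobody is scheduled to ask for it. A reporting duty captures only what the site learns. Section 7.2 allows treatment under a local physician, so the registering site cannot be assumed to see what happens after the last visit.

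Two uses of the data are exposed. The first is the accrual-suspension rule in 16.33, applied cohort by cohort to related grade 4+ non-hematologic toxicity. It is met at 3 or more of the first 10 treated patients, or at 30% thereafter, and it acts on events that are observed. The second is the required reporting of deaths. Patients who stop for severe toxicity are among those who leave observation, so the gap is not confined to patients who are doing well.

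**Working it through.** The plan states no figure to reproduce. The check is a cross-reading plus day counts.

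**Inputs**

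- Cycle 1 lasts 21 days and cycle 6 lasts 28 days (7.1).
- Last scheduled doses in cycle 1: lenalidomide day 14, dexamethasone day 15, pomalidomide day 21 (7.1).
- Last scheduled doses in cycle 6: lenalidomide or pomalidomide day 21, dexamethasone day 22 (7.1).
- Reporting window: 30 days after the last dose (10.41) or last study treatment or procedure (10.6231).
- End of Treatment window: ±7 days (Section 4 table).

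**Assumption.** The documents do not say what the End of Treatment visit is timed from. I take day 21 to 28 for a patient stopping after cycle 1, and day 28 to 35 of cycle 6 for a completer.

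**Formula.** Days without planned contact = (last dose day + 30) − visit day. For a cycle 1 stopper, share = those days ÷ (last dose day + 30).

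| Patient | Last dose | Window closes | Days without planned contact | Share |
|---|---|---|---|---|
| Stops after cycle 1, pomalidomide | day 21 | 21 + 30 = 51 | 51 − 28 = 23 to 51 − 21 = 30 | 23/51 = 45% to 30/51 = 59% |
| Stops after cycle 1, lenalidomide-dexamethasone | day 15 | 15 + 30 = 45 | 45 − 28 = 17 to 45 − 21 = 24 | 17/45 = 38% to 24/45 = 53% |
| Completes cycle 6, IMiD dosed last | day 21 | 21 + 30 = 51 | 51 − 35 = 16 to 51 − 28 = 23 | not computed |
| Completes cycle 6, dexamethasone dosed last | day 22 | 22 + 30 = 52 | 52 − 35 = 17 to 52 − 28 = 24 | not computed |

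If a completer's visit fell at the early edge (28 − 7 = day 21), up to 30 days would be uncovered. For a patient stopping at any other time, a visit 0 to 7 days after the last dose leaves 30 − 7 = 23 to 30 days. Under none of these placements does the visit reach day 30 after the last dose.

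**Effect on the stopping rule.** In a cohort where exactly 3 of the first 10 patients had a qualifying event, missing one leaves 2 of 10, below the threshold. That is true of any 3-of-10 rule. It shows the count is sensitive to one event, not how often an event would be missed.

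**Undefined clock.** Section 7.3 takes completers off study after six cycles but lets them continue their current therapy. For them the documents do not say whether the 30 days run from the last on-study dose or from the last dose ever taken.

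**The case against.** The strongest reply is that the two sets of passages can coexist. Section 4.1 is headed as survival follow-up, says only that follow-up is not required, and may refer to formal follow-up phases, as the schema's abbreviations suggest. Section 10 reporting is triggered by the study team becoming aware of an event. It also contains duties that outlast the schedule, such as following a pregnancy to its outcome. On this reading nothing in Section 10 is cancelled. That stands as far as the duty goes, but it supplies no means of learning of the events, and 13.1 is worded without exception.

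Several stronger conclusions that a reader might draw are not supported:

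- That observation stops at the last dose. The End of Treatment visit includes an adverse event assessment, and footnote 4 of the schedule allows optional samples from patients who stop for intolerable adverse events. Routine care will also reveal some events.
- That 59% of the at-risk period is generally unobserved. That is the upper end for pomalidomide, an option only in cohorts C and D.
- That a 30-day mortality estimate is biased low. Section 16 plans no such estimate.
- That 16.33 would miss any grade 4+ event. It counts only related non-hematologic ones, and accrual may be suspended without the rule being crossed.
- That 10.52 and 9.1 carry the same weight as 10.41 and 10.6231. The 30-day sentences in 10.52 refer to agents under an IND, while Section 15.0 describes the study as IND exempt. Section 9.1 asks for entries in the medical records, not on case report forms.

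**Conclusion.** The inconsistency is real and should be resolved. It rests mainly on 10.41 and 10.6231 set against the schema, 4.1 and 13.1. Under the stated visit timing, a patient stopping after cycle 1 has about 45–59% of the period from first dose to the end of the window without planned contact on pomalidomide, and about 38–53% on lenalidomide-dexamethasone. A completer has about 16 to 24 uncovered days.

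The consequence is possible under-ascertainment of late related grade 4+ non-hematologic events for 16.33, and of deaths that must be reported. How large that would be cannot be derived, because the documents give no miss rate. It would be wrong to conclude that the stopping rule is shown to fail. The primary endpoint, response after one cycle, is unaffected. This is a cheap improvement to safety ascertainment, not a flaw in the trial's main estimate.

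**What to change.** Reconcile the schema, 4.1 and 13.1 with Sections 9.1 and 10:

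- Add one safety contact, by telephone or chart review, to the Section 4 table 30 days after the last on-study dose for every treated patient, including those who stop early for toxicity.
- State that off-study status takes effect after that contact.
- Define the last dose, for this purpose, as the last dose given on study, so that the clock is fixed for patients who continue the drugs after cycle 6.
- State what the End of Treatment visit is timed from.

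The cost is a short amendment and one contact for each of up to 190 patients (the maximum accrual in 16.22). No change to the sample size or the analysis is needed.

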5.0 Grouping Factor

5.1 Multiple Myeloma Cohort: Cohort A (Smoldering MM), Cohort B (Newly Diagnosed MM), Cohort C (Relapsed/Refractory MM) and Cohort D (Relapsed on Len maintenance).

6.0 Registration Procedures

6.1 Registration:

6.21 Registering a patient

To register a patient, access the Mayo Clinic Research Registration Application web page. The registration/ randomization application is available 24 hours a day, 7 days a week. Back up and/or system support contact information is available on the website. If unable to access the website, call Research Site Management at [contact] between the hours of 8 a.m. and 4:30 p.m. Central Time (Monday through Friday).

The instructions for the registration/randomization application are available on the Mayo Clinical Office of Clinical Trials web page (<https://www.mayo.edu/research/centers-programs/center-clinical-translational-science/offices/office-of-clinical-trials/research-registration-application>) and detail the process for completing and confirming patient registration. Prior to initiation of protocol treatment, this process must be completed in its entirety and an MCCC subject ID number must be available as noted in the instructions. It is the responsibility of the individual registering the patient to confirm the process has been successfully completed prior to release of the study agent. Patient registration via the registration/randomization application can be confirmed in any of the following ways:

- Contact Mayo Clinic Research Site Management at [contact]. If the patient was fully registered, the Research Site Management staff can access the information from the centralized database and confirm the registration.
- Refer to “Instructions for Remote Registration” in section “Finding/Displaying Information about A Registered Subject.”

6.2 Verification of materials

Prior to accepting the registration, registration/randomization application will verify the following:

- IRB approval at the registering institution
- Patient eligibility
- Existence of a signed consent form
- Existence of a signed authorization for use and disclosure of protected health information

6.3 Documentation of IRB approval

Documentation of IRB approval must be on file in the Registration Office before an investigator may register any patients.

In addition to submitting initial IRB approval documents, ongoing IRB approval documentation must be on file (no less than annually) with Research Site Management ([contact] or email [contact]). If the necessary documentation is

not submitted in advance of attempting patient registration, the registration will not be accepted and the patient may not be enrolled in the protocol until the situation is resolved.

When the study has been permanently closed to patient enrollment, submission of annual IRB approvals to the Registration Office is no longer necessary.

6.4 Correlative Research

6.41 Mandatory

A mandatory correlative research component is part of this study, the patient will be automatically registered onto this component (see Sections 3.19b and 14.0).

6.5 Treatment start

Treatment cannot begin prior to registration and must begin ≤ 28 days after registration.

6.6 Baseline symptoms

All required baseline symptoms (see [Section 10.6](#)) must be documented and graded.

6.7 Study Conduct

The clinical trial will be conducted in compliance with regulations (21 CFR 312, 50, and 56), guidelines for Good Clinical Practice (ICH Guidance E6), and in accordance with general ethical principles outlined in the Declaration of Helsinki; informed consent will be obtained from all participating patients; the protocol and any amendments will be subject to approval by the designated IRB prior to implementation, in accordance with 21 CFR 56.103(a); and subject records will be stored in a secure location and subject confidentiality will be maintained. The investigator will be thoroughly familiar with the appropriate use of the study drug as described in the protocol and Investigator's Brochure. Essential clinical documents will be maintained to demonstrate the validity of the study and the integrity of the data collected. Master files should be established at the beginning of the study, maintained for the duration of the study and retained according to the appropriate regulations.

7.0 Protocol Treatment

7.1 Treatment Schedule

Cohort A and B Cycle 1

Treatment medication table. Patient may receive Lenalidomide OR Lenalidomide + Dexamethasone.

Agent	Dose Level	Route	Day	Re Rx
Lenalidomide	25 mg*	Oral	Cycle 1: Day 1-14	Cycle 1: 21 days
Dexamethasone	40 mg**	Oral	Cycle 1: Day 1 ,8, ,15	Cycle 1: 21 days

Cycle 1 length = 21 days

* Starting dose will be determined as per the creatine clearance below (see 7.12)

**The dose of dexamethasone used can be determined by the treating physician and omitted if needed.

Cohort C and D Cycle 1

Treatment medication table. Patient may receive Lenalidomide + Dexamethasone OR Pomalidomide + Dexamethasone.

Agent	Dose Level	Route	Day	ReRx
Lenalidomide	25 mg*	Oral	Cycle 1: Day 1-14	Cycle 1: 21 days
Pomalidomide	4 mg	Oral	Cycle 1: Day 1-21	Cycle 1: 21 days
Dexamethasone	40 mg**	Oral	Cycle 1: Day 1 ,8, ,15	Cycle 1: 21 days

Cycle 1 length = 21 days

* Starting dose will be determined as per the creatinine clearance below (see 7.12)

** The dose of dexamethasone used can be determined by the treating physician and omitted if needed.

Cohort A and B Cycles 2-6

Treatment Medication Table. Patient may receive Lenalidomide based regimens.

Agent	Dose Level	Route	Day	Re Rx
Lenalidomide	25 mg*	Oral	Cycle 2-6: Day 1-21	Cycles 2-6: 28 days
Dexamethasone	40 mg**	Oral	Cycle 2-6: Day 1 ,8, ,15, 22	Cycles 2-6: 28 days

Note: Standard of care agents can be added for cycles 2-6 as long as the regimen contains lenalidomide

Cycles 2-6 length = 28 days

* Any dose-adjustments will be determined as per the creatine clearance below (see 7.12).

** The dose of dexamethasone used can be determined by the treating physician and omitted if needed.

Cohort C and D Cycles 2-6

Treatment medication table. Patient may receive Lenalidomide based regimen OR Pomalidomide based regimen.

Agent	Dose Level	Route	Day	ReRx
Lenalidomide	25 mg*	Oral	Cycles 2-6: Day 1-21	Cycles 2-6: 28 days
Pomalidomide	4 mg	Oral	Cycles 2-6: Day 1-21	Cycles 2-6: 28 days
Dexamethasone	40 mg**	Oral	Cycle 2-6: Day 1,8,15,22	Cycles 2-6: 28 days

Note: Standard of care agents can be added for cycles 2-6 as long as the regimen contains lenalidomide or pomalidomide

Cycles 2-6 length = 28 days

* Any dose-adjustments will be determined as per the creatinine clearance below (see 7.12).

** The dose of dexamethasone used can be determined by the treating physician and omitted if needed.

7.12

Creatinine Clearance (CrCl)	Lenalidomide Dose
CrCl >60 ml/minute	25 mg No adjustment required
CrCl 30-60 ml/minute	10 mg once daily (may increase to 15 mg once daily after 2 cycles if nonresponsive but tolerating treatment)
CrCl <30 ml/minute (non-dialysis dependent)	15 mg every 48 hours

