2.0 Goals

2.1 Primary Goal

To determine response rates (>=PR) of prospectively treated MM patients with one cycle of therapy containing a combination of an immunomodulator and dexamethasone.

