16.2 Statistical Design

Due to the lack of data to identify relevant biomarkers, the estimation of RR would be of interest. In each group, the response rates will be examined to see if there's any preliminary evidence to suggest further studies. This study will not utilize a formal statistical design.

For each biomarker category, the RR will be estimated by the number of patients who achieve a PR or better divided by the total number of evaluable patients in each cohort. Exact binomial 95% confidence intervals for these rates will be calculated.

16.22 Sample Size: A maximum of 30 evaluable patients will be accrued in cohort A and B and 60 patients in cohort C and D respectively. We anticipate accruing an additional 2 in cohort A and B and 3 in cohort C and D to account for ineligibility, cancellation, major treatment violation, or other reasons. Therefore, the maximum projected accrual is 190 patients (A: 32, B: 32, C: 63 and D: 63).

16.23 Accrual Rate and Study Duration: The anticipated accrual rate is 6 evaluable patients per month. Therefore, the accrual period for this pilot study is expected to be approximately 32 months. The final analysis can begin approximately 35 months after the trial begins, i.e. as soon as the last patient has been observed for 1 months and allowing 2 months for data entry.

16.24 Other considerations: Adverse events, quality/duration of response, and patterns of treatment failure observed in this study, as well as scientific discoveries or changes in standard care will be taken into account in any decision to terminate the study

16.3 Analysis Plan.

The analysis for this study is planned to start after data maturity has occurred. It is anticipated that the earliest date in which the result will be available via manuscript, abstract or presentation after the last registered patient has been followed for at least 1 month.

16.31 Primary Outcome Analyses:

Each cohort (A-D) will be evaluated separately and independently.

16.311 Definition:

The primary endpoint of this study is RR after 1 cycle of treatment. RR is defined as a binary variable. A success will be defined as patient who achieve a response of a PR or better using the IMWG criteria (Section 11.0) after one cycle of treatment. All patients meeting eligibility criteria who have signed a consent form, who complete at least one cycle of treatment and have successfully submitted biospecimens (pre and post treatment) will be evaluable for the endpoint.

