Estimation: For each biomarker of interest, RR will be calculated by the number of successes divided by the total number of evaluable patients in each cohort.

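### The primary response rate is meant for an immunomodulator plus dexamethasone, but patients treated without dexamethasone count in it and no planned analysis separates them

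*Combined protocol and SAP*

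**What the plan says.** Section 2.1 states the primary goal: "To determine response rates (>=PR) of prospectively treated MM patients with one cycle of therapy containing a combination of an immunomodulator and dexamethasone". Section 16.1 repeats the same target, and the rationale in 1.2 describes a first cycle made up only of an IMiD and dexamethasone.

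Section 7.1 permits more than that in cycle 1:

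- Cohorts A and B: "Patient may receive Lenalidomide OR Lenalidomide + Dexamethasone".
- Cohorts C and D: "Patient may receive Lenalidomide + Dexamethasone OR Pomalidomide + Dexamethasone".
- Footnote to the tables of all four cohorts: "The dose of dexamethasone used can be determined by the treating physician and omitted if needed".

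On the analysis side, section 16.311 takes as evaluable the eligible, consented patients "who complete at least one cycle of treatment and have successfully submitted biospecimens (pre and post treatment) will be evaluable for the endpoint". The estimator is: "RR will be calculated by the number of successes divided by the total number of evaluable patients in each cohort". It is applied for each biomarker of interest, and section 16.31 adds: "Each cohort (A-D) will be evaluated separately and independently".

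**The concern.** A patient in Cohort A or B who takes lenalidomide alone through cycle 1 follows the protocol, can be evaluable, and counts in full toward a rate that the goal attributes to the combination. The footnote opens the same route in Cohorts C and D. The reported rate is then an average over treatments with and without dexamethasone, weighted by how often physicians left dexamethasone out. The plan does not predict that weight and does not commit to reporting it. A reader could not tell whether a low rate in a cohort reflects the doublet or the share of patients who did not get it.

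The same gap reaches the secondary aim of finding markers that predict response (2.2, 16.321). If the choice of regimen happened to be related to a marker, part of that marker's association with response could come from the treatment given.

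**Working it through.** **1. The plan's own figures.** There is no power calculation and no target rate or precision to reproduce. The accrual total does reproduce: 32 + 32 + 63 + 63 = 190, and 190 / 6 per month = 31.7, stated as about 32 months. The denominators that matter here are 30 evaluable patients in each of A and B, and 60 in each of C and D (16.22).

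**2. Does any part of the plan separate the regimens?** I looked in each place that could.

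| Place | What it uses | Regimen? |
|---|---|---|
| 5.1 Grouping factor | cohort | no |
| 12.0 Descriptive factors | prior treatment, response parameter, FISH risk | no |
| 13.5 Major violation | severe breach of cycle-1 treatment requirements | permitted omission is not a breach |
| 16.311 Evaluable set | eligibility, consent, one cycle, paired samples | no dexamethasone requirement |
| 16.2 and 16.311 Estimator | all evaluable patients in the cohort | no |
| 16.321 and 16.323 Models | biomarkers and response | none named |

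None of them does.

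**3. Size of the dilution.** Let r be the rate with dexamethasone, s the share treated without it, and d the number of points by which the rate is lower without it. Then

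pooled rate = (1 − s)·r + s·(r − d) = r − s·d,

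so the shift is s·d whatever r is. The documents give neither s nor d. The values below are assumptions, including the assumption that d is positive.

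| Share without dexamethasone | d = 10 | d = 20 | d = 30 | d = 40 |
|---|---|---|---|---|
| 10% | 1 | 2 | 3 | 4 |
| 25% | 2.5 | 5 | 7.5 | 10 |
| 50% | 5 | 10 | 15 | 20 |

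(Points by which the pooled rate falls below the combination rate.)

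For scale, the exact 95% interval at 15/30 is 31.3–68.7% (half-width 18.7 points), and at 30/60 it is 36.8–63.2% (half-width 13.2). In a 30-patient cohort only the most extreme cell, 20 points, exceeds the half-width. The interval does not cover this shift, however, because it describes sampling error around the mixed rate.

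**4. The two IMiDs in C and D.** Section 1.1 quotes overall response of 48–61% for lenalidomide in one set of previously treated patients and 35–42% for pomalidomide at 4 mg. These are not presented as one-cycle rates and come from different studies, so they serve only as illustration. An even split would give (48 + 35)/2 = 41.5% to (61 + 42)/2 = 51.5%. Moving from all lenalidomide to all pomalidomide would shift the rate by 48 − 42 = 6 to 61 − 35 = 26 points. This shows that the IMiD mix is worth reporting. It does not show a conflict with the goal.

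**5. Precision of split rows.** Exact 95% intervals: 3/6 gives 11.8–88.2%; 4/9 gives 13.7–78.8%; 10/20 gives 27.2–72.8%. In a 30-patient cohort, 6 and 9 patients correspond to 20% and 30% treated without dexamethasone.

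**The case against.** The strongest reply is that this is an estimation-only pilot with no formal design. No test, error rate or decision threshold on the primary endpoint is affected. That is true, and it limits the point to what the primary rate means.

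Three stronger readings are tempting, and the documents do not support them.

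- A reader might infer that pooling lenalidomide and pomalidomide also contradicts the goal. It does not. The goal names a class, "one cycle of therapy containing a combination of an immunomodulator and dexamethasone", and either drug with dexamethasone satisfies it. Separating the two is a matter of interpretability.
- A reader might infer that regimen confounds the biomarker results. The documents do not say how physicians choose the IMiD, and on dexamethasone they say only that it may be omitted if needed. Section 16.2 says relevant biomarkers are not yet known. Confounding is possible, not shown.
- A reader might infer that the reported rate will certainly understate the combination. If few patients go without dexamethasone, the shift is small; if none do, it is zero. All sizes in the dilution table rest on assumed values.

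It can also be said that restricting the goal 2.1 estimate to combination patients selects on a physician's choice and shrinks the denominator. That stands. It is why the all-evaluable rate should stay beside it, and why differences between regimen rows should not be read as the effect of dexamethasone.

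**Conclusion.** The mismatch is real and follows from the text alone: the goal names the combination, the treatment section allows patients to go without dexamethasone, and the analysis counts them without distinction. It is plainest in Cohorts A and B, where lenalidomide alone is a listed option; in C and D it arises only through the omission footnote. Rates are planned per biomarker within cohort, so the defect is the missing split by regimen at every level, not a single rate per cohort.

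The size cannot be fixed from the documents. Under the assumed ranges (10% to 50% without dexamethasone, 10 to 40 points lower response) the primary rate falls short of the combination rate by 1 to 20 points. The correction should be made because it is cheap and determines what the primary result describes. It is not a threat to the validity of the trial as a pilot.

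**What to change.** Leave the treatment flexibility as it is, and reconcile 2.1 and 16.1 with 7.1 so that the stated target and the permitted regimens agree. Then:

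- **16.31:** keep the all-evaluable rate in each cohort. Beside it, report the cycle-1 rate with exact 95% interval by cycle-1 regimen, defined as the regimen started on Day 1: IMiD plus dexamethasone versus IMiD alone in every cohort, and also by IMiD in C and D (which gives pomalidomide alone a row). Give the number of patients in each row.
- **Goal 2.1:** use the IMiD-plus-dexamethasone row as its estimate.
- **16.321:** as a sensitivity analysis where numbers allow, add dexamethasone use, plus IMiD in C and D only. In A and B the cycle-1 IMiD is always lenalidomide, so that term would be constant. With 30 patients and about 15 responders at a 50% rate, there is little room for extra terms.

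The Day 1 definition avoids reclassifying patients after events during the cycle. Its price is that a patient who starts dexamethasone and later omits it still counts as combination.

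The cost is a few lines of text and table rows, with no change to sample size or care. A medication diary is scheduled (4.0) and local physicians must document administration (7.2), so the regimen should be obtainable. The case report forms are not in the documents, so confirm that they capture Day 1 dexamethasone. The main downside is imprecision: about 12–88% at 3/6 and 27–73% at 10/20, against 31–69% at 15/30. The split rows are descriptive only.
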